24 HOURS AND 48 HOURS POST-PROCEDURE EVALUATIONS

The subject will be required to record the following at home on the forms provided by the test site at 24 hours and again at 48 hours after completion of the procedure administration phase at the test site.

OUTCOME ASSESSMENTS

- Visual Analog Scale (VAS) Degree of Pain Rating
- Linear Range of Motion (ROM)
- Subject Satisfaction with Study Outcome Rating
- Adverse Events Evaluation

ADVERSE EVENTS

At each evaluation point throughout the clinical study, and at any other time throughout the duration of the clinical trial that is necessary, any and all potential adverse events reported by a subject or observed by an investigator will be recorded on the case report form, and subsequently evaluated by a suitably qualified independent reviewer for determination of relationship to the study treatment and whether or not any corrective action needs to be taken. All potential adverse events recorded will be appropriately reported to the governing IRB, as applicable.

It is unlikely and not expected that any adverse events will result from implementation of this clinical study protocol. Prior clinical trials using low level laser light have not typically yielded any adverse events or reactions. However, potential adverse events that may feasibly occur from application of the Erchonia® GVL include, but are not necessarily limited to: skin irritation, discoloring, rash, indentations and infection.

PRIVACY AND CONFIDENTIALITY

Records for each subject in this clinical study will be maintained in separate files in a locked filing cabinet at the respective test site. The investigator at the test site will be responsible for ensuring that all records for a subject pertaining to his or her participation in the clinical study are stored in that subject's file at all times other than when information is being recorded on them.

Copies of all of the subject case report forms will be made and supplied to Regulatory Insight, Inc. and Erchonia Corporation. Regulatory Insight, Inc. and Erchonia Corporation will maintain these copies in a separate clinical study file that is kept in a locked filing cabinet at their respective premises. The original records will be maintained at the respective test sites.

Subjects' identities will be kept confidential by assigning each subject a subject ID upon acceptance into the study. The subject ID will comprise the investigator's two initials (first and last name initials) and a three-digit number that will be based upon the subject's order of entry into the clinical study. Each test site will be assigned a unique range of numbers. Test site #1 will be assigned numbers 001 to 100 (Subject ID RS001 to RS100). Test site #2 will be assigned numbers 101 to 200 (Subject ID AC101 to AC200). Test site #3 will be assigned numbers 201 to 300 (Subject ID KG101 to KG200). For example, the eighth subject to be enrolled at test site #2 would have a subject ID of AC108. Neither the study Sponsor nor Regulatory Insight, Inc. will receive any additional identifying information about a subject and will therefore have no way of linking a Subject ID to a particular subject and his or her results.

STATISTICAL ANALYSIS PLAN

PRIMARY EFFICACY OUTCOME MEASURE: CHANGE IN SUBJECT SELF-REPORTED VAS PAIN RATING FROM BASELINE TO STUDY ENDPOINT

The primary efficacy outcome measure for this clinical study is the change in subject self-reported Visual Analog Scale (VAS) pain rating from baseline to study endpoint evaluation, with study endpoint defined as within 3 minutes of completion of the study single procedure administration with the Erchonia® GVL laser.

Individual Subject Success Criteria

Individual subject success criteria is defined as a 30% or greater decrease in self-reported VAS pain rating at study endpoint relative to baseline.

Overall Study Success Criteria.

Overall study success criteria is defined as at least $75\% \pm 5\%$ of subjects (70% to 80%) meeting the study individual success criteria.

Justification for Study Success Criteria

The clinical relevance and statistical justification of the individual subject and overall study success criteria is as follows:

- This study is established as a non-inferiority study, such that the research hypothesis is that green / violet dual-diode therapy with the Erchonia® GVL is either equivalent to or superior to red / violet dual-diode therapy with the Erchonia® EVRL in effecting a clinically meaningful temporary reduction in neck and shoulder pain of musculoskeletal origin when compared with the data attained from the red / violet dual-diode Erchonia® EVRL clinical trial conducted in 2019 (comparative reference study) whose results successfully supported 510(k) clearance of K191257, given that the application and evaluation of the Erchonia® GVL in the current study is intended to support clearance of the Erchonia® GVL for the identical indication as the Erchonia® EVRL.

Therefore:

- The individual subject success criteria in this clinical study as specified above is selected to be identical to that of the comparative reference study.
- The overall study success criteria in this clinical study is determined based on the actual proportion of individual subject successes attained during the comparative reference trial of 75%. The $\pm 5\%$ is the selected equivalence margin (δ), the maximally clinically acceptable difference for which the range of values (70% to 80%) for which the efficacies are “close enough” to be considered equivalent.
- Non-inferiority is established to be attained if the proportion of study subjects in this GVL study who meet the individual subject success criteria is no more than 5% less than the proportion of study subjects in the comparative reference EVRL study who met the same individual success criteria, i.e., no less than 70%.

This strategy is the identical strategy employed in the clinical study for the Erchonia® EVRL in red / violet dual-diode mode whose results supported FDA clearance of K191257 based on the same equivalency criteria to the comparative reference group of the active treatment arm of the Erchonia® EVRL in red-diode only mode that had previously received FDA clearance under K012580 and K152196, for the identical indication.

Hypotheses

- *Null Hypothesis:* Treatment application of the Erchonia® GVL in simultaneous green / violet dual-diode mode is inferior to treatment application of the Erchonia® EVRL in simultaneous red / violet dual-diode mode in reducing neck and shoulder pain of musculoskeletal origin.
- *Alternative Hypotheses:* Treatment application of the Erchonia® GVL in simultaneous green / violet dual-diode mode is NOT inferior to treatment application of the Erchonia® EVRL in simultaneous red / violet dual-diode mode only in reducing neck and shoulder pain of musculoskeletal origin.

Evaluation Time Point

Study endpoint evaluation is established as immediately (within 3 minutes) following the study single procedure administration. Study success analysis is established at study endpoint relative to baseline.

The study endpoint evaluation for this study was established to be identical to that in the reference comparative study.

Populations Examined

Primary analysis of efficacy will be according to intent to treat (ITT) analysis (including all enrolled subjects) supported by per protocol (PP) analysis (including only subjects who completed the study according to the full protocol). Non-inferiority will be established if both the ITT and PP analyses agree.

Handling of Missing Data

Missing data for the ITT population will be handled through Last Observation Carried Forward (LOCF): by carrying forward the last recorded observation to fill in the subsequent missing value

PRIMARY EFFICACY OUTCOME STATISTICAL EVALUATION

Primary efficacy outcome success will be determined as follows:

Proportion of Successes

- The percentage of individual subject successes in this clinical study will be calculated according to the pre-specified criteria of a decrease in VAS pain ratings of 30% or greater from baseline to endpoint evaluation.
- **Primary study success will be considered met, i.e., non-inferiority will be established, according to the pre-specified overall study success criteria, if this proportion is not less than 70%.**

Comparison of Proportions

A comparison of proportions test will be performed to evaluate if the two success proportions (GVL vs. EVRL) are equivalent to support the conclusion of the proportions of successes analysis. Significance levels will be considered at the $p<0.05$ level.

Change Scores

- T-test analysis of the difference in the mean change in VAS levels from baseline to endpoint between the dual-diode and red only diode treatment administration groups. Significance levels will be considered at the p<0.05 level.
- A t-test for two independent sample will be performed to evaluate the significance of the difference in the mean change in VAS pain scores from baseline to endpoint evaluation between the two study groups (GVL vs EVRL) to evaluate for equivalency to support the support the conclusion of the proportion of successes evaluation. Significance levels will be considered at the p<0.05 level.

SECONDARY EVALUATIONS

The following secondary evaluations will be performed on the GVL study data set. As no claims are intended to be made based on the secondary measures, the findings are presented through descriptive analysis and qualitative trending only, without evaluation for or claims of statistical significance.

- Change in mean VAS ratings across study duration: all study evaluation points (baseline, endpoint, 24 hours and 48 hours post-procedure).
- Change in linear ROM measurements across respective study evaluation points at study baseline and endpoint.
- Subject satisfaction with study outcome ratings across study duration.

INDIVIDUAL TEST SITES

Results will be presented by individual test site for comparison.

INDIVIDUAL SUBJECT RESULTS

Individual subject results for study outcome measures will also be presented.

SAFETY ANALYSES

Safety analyses will be based on all enrolled subjects and will be assessed by evaluating and comparing frequency and incidence of observed and/or reported adverse events between subjects in the GVL and the EVRL studies. A chi-square test with a continuity correction will be performed to compare the percentage of subjects who had adverse events between the two subject groups.

INFORMED CONSENT

- Informed consent will be an agreement between the individual investigator and each subject, having the capacity to understand and make an informed decision. Consent will be obtained prior to each potential subject's participation in this clinical study.
- Each subject participating in this clinical study will be made aware of the fact that his or her participation involves research and the intent of the research, the expected duration of his or her participation and a description of the procedures that will be followed.
- Each subject will be made aware of the reasonably expected benefits he or she might receive, as well as any risks or potential discomfort that are involved.
- Each subject will also be made aware of alternative treatments available to him or her.
- Each subject will be made aware that his or her records will remain confidential, but that the FDA and the IRB has the right to inspect his or her records.
- Each subject will be told that his or her participation in the clinical study is voluntary, without force or influence from the investigator or sponsor.
- Each subject will be given the name and method of contacting the appropriate person(s) to answer his or her questions about the research and in the event of a research-related injury.

The informed consent form that will be used to collect the data from each subject in this clinical study can be found in **Appendix B**.

CASE REPORT FORMS

The case report forms that will be used to collect the data from each subject in this clinical study can be found in **Appendix C**.

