This study is to see if the Erchonia® GVL, a non-invasive, investigational device that uses low-level laser light, can help to relieve neck and shoulder pain that has been ongoing for at least 30 days.

The study involves a single visit to the test site and recording some information at home for two more days.

Please contact <PI name> at
<test site name & location> at
<phone and/or e-mail> for details.

Compensation

A subject will not receive financial or any other form of compensation to participate in this clinical study. However, he or she will also not be charged for the cost of the study procedure with the Erchonia® GVL Laser or for the cost of any other directly-related evaluations or measurements that occur as a directly-associated part of his or her participation in the study.

STUDY PROCEDURE

STUDY TEST BATTERY

The following are the study measurement and assessment tools to be used and the variables to be recorded in this clinical study. At each evaluation point, the precise tools and variables that will be employed will be specified.

QUALIFICATION EVALUATION TOOL

PHYSICAL EXAMINATION

- (i) Inspection: Manipulation of the neck, shoulders, and cervical spine to evaluate for knots (muscle spasms), tightness, swelling, osteophytes, etc.
- (ii) Palpation Assessment: Physical assessment of the bony and soft tissues of the neck, shoulder, and cervical spine through touch with the pads of the fingers, to evaluate for muscle tightness and knotting, trigger points that cause pain and possibly also radiating pain.
- (iii) Range of Motion (ROM) Assessment: ROM will be evaluated through active, passive, and manual resistance to evaluate for pain and pain worsening and weakness.
 - a) *Neck ROM*: Neck ROM will be evaluated across the six cardinal planes:
 - Sagittal plane: flexion (max. 90°) and extension (max. 25°)
 - Frontal plane: right lateral flexion and left lateral flexion (max. 45°)
 - Transverse plane: right rotation and left rotation (max. 80°)
 - b) *Shoulder ROM*:
 - Right and left abduction (max 150°)
 - Right and left adduction (max. 30°)
 - Right and left extension (max 50°)
 - Right and left flexion (max. 50°)

BASELINE VARIABLES

NECK/SHOULDER PAIN VARIABLES

- (i) Location of pain: right side/left side/back of neck; right/left shoulder
- (ii) Duration of pain: months/years since onset of first episode of neck/shoulder pain

CONCOMITANT MEDICATION AND THERAPY USE

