 14. Step 10 is then repeated to the left sternocleidomastoid and scalenus muscles.
 15. The subject's protective eyewear is removed, and the single procedure administration session is over.

Justification for the Procedure Administration Protocol

The procedure administration protocol in this current study is identical to that which was evaluated in the comparative retrospective EVRL study to enable direct comparison of findings between the two studies and statistical analysis of different group outcomes.

PROCEDURE ADMINISTRATION PHASE EVALUATIONS: STUDY ENDPOINT

Within 3 minutes of completion of the procedure administration phase, study endpoint evaluation will occur.

OUTCOME ASSESSMENTS

- Visual Analog Scale (VAS) Degree of Pain Rating
- Linear Range of Motion (ROM)
- Subject Satisfaction with Study Outcome Rating
- Adverse Events Evaluation

POST-PROCEDURE ACTIVITIES

The post-procedure evaluation phase of this study will commence immediately following completion of the procedure administration phase evaluations and will last for 2 days (48 hours).

The post-procedure outcome assessments will be recorded by the subject in his or her own home on forms provided by the test site. The subject will be instructed on when and how to complete the forms and how to return them to the test site prior to leaving the test site on the procedure administration day.

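### The per-protocol set has no cut-off at the 3-minute primary endpoint, so a missing 24- or 48-hour home form can remove a subject with complete primary data from a set that must support non-inferiority

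*Combined protocol and SAP*

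**What the plan says.** **Endpoint.** The SAP (Primary Efficacy Outcome Measure; Evaluation Time Point) sets the primary assessment within 3 minutes of the procedure and adds: "Study success analysis is established at study endpoint relative to baseline".

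**Analysis sets.** Under Populations Examined, ITT (all enrolled subjects) is the primary analysis. PP supports it and is described as "including only subjects who completed the study according to the full protocol". The section gives no time limit and no list of deviations. It then says: "Non-inferiority will be established if both the ITT and PP analyses agree".

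**Success rule.** Under Proportion of Successes, the bold rule reads "non-inferiority will be established, according to the pre-specified overall study success criteria, if this proportion is not less than 70" percent. That sentence names no analysis set.

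**Follow-up.** Post-Procedure Activities describes a 48-hour phase of the study that begins after the endpoint evaluations. The section on the 24- and 48-hour evaluations says: "The subject will be required to record the following at home on the forms provided by the test site at 24 hours". The same recordings are due a second time at 48 hours. The newspaper advertisement tells recruits: "The study involves a single visit to the test site and recording some information at home for two more days". Secondary Evaluations counts both later times within the study duration, but treats these data as descriptive and supporting no claim.

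**Range of motion.** Linear ROM is on the list of home recordings. The Study Test Battery measures it with an inclinometer, the shoulder by passive abduction. Secondary Evaluations analyses ROM only at baseline and endpoint.

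**The concern.** A PP set should remove subjects whose primary result cannot be trusted as a test of the treatment. A form not returned a day or two later says nothing about a VAS mark made within 3 minutes of the procedure. As worded, such a subject has not completed everything the protocol requires and so leaves PP. Data that support no claim can then decide who counts in a set on which the non-inferiority verdict depends.

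The ROM entry makes this more than a matter of a few lost forms. If a home ROM reading is part of completing the protocol, and subjects cannot take it as the Study Test Battery describes, a literal reading could exclude many of them. Those passages need to be reconciled whatever is decided about PP.

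At stake is a success missed because of events after the primary assessment, or a decision about who is in PP that is taken only once results are known.

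**Working it through.** **Inputs from the documents.** Planned enrolment is 43 (Sample Size). The reference success proportion is 75% and the margin 5 percentage points (Justification for Study Success Criteria). The bar reproduces: 75% − 5% = 70%.

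**Inputs assumed.** The documents give no missing-form rate, so the number k of subjects excluded from PP for late events is assumed, from 0 to 8. Exclusions are taken as unrelated to outcome. The true success rate is taken as 75%, with 80% as a second case.

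**Step 1: lowest passing counts.** ITT needs 31 successes, since 30/43 = 69.8% fails and 31/43 = 72.1% passes. The PP minimum is the smallest whole number not below 0.70 × (43 − k):

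| k | 0 | 1 | 2 | 3 | 4 | 5 | 6 | 7 | 8 |
|---|---|---|---|---|---|---|---|---|---|
| PP size | 43 | 42 | 41 | 40 | 39 | 38 | 37 | 36 | 35 |
| PP minimum | 31 | 30 | 29 | 28 | 28 | 27 | 26 | 26 | 25 |

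**Step 2: when an ITT pass can be lost.** Suppose every excluded subject is a responder.
- With k = 3, 31 − 3 = 28 and 28/40 = 70.0%, which still passes. No ITT pass can be lost with three or fewer exclusions, random or not.
- With k = 4, 31 − 4 = 27 and 27/39 = 69.2%, which fails. 32 − 4 = 28 and 28/39 = 71.8% passes.
- For k = 4 to 6, only an ITT count of 31 is exposed. For k = 7 or 8, a count of 32 (74.4%) is too: 32 − 7 = 25, below 26, and 32 − 8 = 24, below 25.

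**Step 3: probability.** Let X ~ Binomial(43, p) be the ITT successes and, given X = x, let R ~ Hypergeometric(43, x, k) be the responders excluded. Sum P(X = x) × P(R = r) over x ≥ 31 with x − r below the PP minimum.

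For k = 4 and p = 0.75:
- P(X = 31) = C(43,31) × 0.75^31 × 0.25^12 = 12.2%.
- P(all four excluded are responders) = C(31,4)/C(43,4) = 31,465/123,410 = 25.5%.
- The product is 3.1%.

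For k = 7 and p = 0.75:
- P(X = 32) = 12.2% × (12/32) × 3 = 13.8%.
- PP fails with probability 35.6% given x = 31 and 10.4% given x = 32.
- 12.2% × 35.6% + 13.8% × 10.4% = 5.8%.

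| P(ITT passes, PP fails) | k = 0–3 | k = 4 | k = 5 | k = 6 | k = 7 | k = 8 |
|---|---|---|---|---|---|---|
| true rate 75% | 0 | 3.1% | 2.2% | 1.5% | 5.8% | 4.3% |
| true rate 80% | 0 | 1.6% | 1.1% | 0.8% | 3.2% | 2.4% |

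The figures do not rise steadily with k because the minimum count is a whole number.

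**Step 4: effect on success.** At a true rate of 75%, ITT alone passes with probability 73.7%. If both sets must pass, this becomes 73.7% − 3.1% = 70.6% (k = 4) or 73.7% − 5.8% = 67.9% (k = 7).

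**Step 5: after the fix.** A missing late form no longer removes anyone, so k from this cause is 0 and the loss is 0.

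**The case against.** No sentence says that a missing 24- or 48-hour form removes a subject from PP. Success analysis is fixed at the endpoint, so the sponsor could take the full protocol to end there. That is a reasonable intention, but the PP definition does not state it, and the sections on follow-up put the home recordings inside the study as a requirement. This part of the objection lowers the severity but does not remove the gap.

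The stronger part of the objection is that the plan already protects the verdict. ITT is primary, the two analyses must agree, and a disagreement costs only the sponsor. That stands, and it rules out several stronger readings that a reader might infer:

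- *That the plan leaves the outcome open if ITT and PP differ.* The agreement sentence says if rather than only if, but its plain sense is that non-inferiority is then not established.
- *That PP alone could turn an ITT failure into a success*, for example 30/43 = 69.8% becoming 30/42 = 71.4% when one non-responder is excluded. ITT is primary, agreement is required, and the success criteria define the 70% bar over the study's subjects. A PP-only pass contradicts these together.
- *That every ITT/PP disagreement counts as harm.* Where ITT has already failed, a PP pass changes no verdict, so only ITT-passes/PP-fails is counted above.
- *That late exclusions bias the result through pain response.* The undertaking to refrain from pain medication is an eligibility criterion, not a PP exclusion rule, and the documents show no such dependence or direction.

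**Conclusion.** The PP definition lacks a cut-off at the primary endpoint and, applied as written, excludes subjects with complete primary data from a set that must agree with ITT. The consequence is limited: a lost success when the ITT count is 31 (or 32 with seven or eight exclusions). Its probability is nil for three or fewer exclusions. For four to eight it is 1.5% to 5.8% at a true rate of 75% and 0.8% to 3.2% at 80%. These figures rest on assumed exclusion counts, random exclusion, and the reading that both sets must reach 70%. A literal reading of the home ROM requirement could push exclusions beyond that range. On the documents' text the defect cannot produce a false claim of non-inferiority. Severity: minor.

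**What to change.** 1. Define PP for the primary endpoint by conditions up to that endpoint only: eligibility met, full procedure received, baseline and 3-minute VAS recorded, and no major protocol deviation before the 3-minute assessment. State that a missing 24- or 48-hour form does not remove a subject.
2. As a clarification, repeat the agreement condition in the bold success rule: not less than 70% in both the ITT and PP sets.
3. Reconcile the home ROM entry with the inclinometer method and with the secondary analysis, which uses ROM at baseline and endpoint only.

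The first two changes take a few sentences in the SAP, and the third is an edit to the protocol text. None adds subjects, visits or data. The 24- and 48-hour VAS and satisfaction data can still be collected and described as planned.

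### Non-inferiority is declared on an observed success rate of at least 70% (31 of 43) with no confidence limit or test against the 5-point margin, so a device exactly on the margin passes 45.6% of the time

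*Combined protocol and SAP*

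**What the plan says.** Under Justification for Study Success Criteria the plan declares its aim: "This study is established as a non-inferiority study, such that the research hypothesis is that" GVL is equivalent or superior to EVRL. The overall criterion is "determined based on the actual proportion of individual subject successes attained during the comparative reference trial of 75" per cent, with 5 points as the margin. The rule follows directly: "Non-inferiority is established to be attained if the proportion of study subjects in this GVL study who meet the individual subject success criteria" lies at most 5 points below the EVRL proportion, which the plan equates with no less than 70%. Hypotheses then sets out a null of inferiority.

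Proportion of Successes, under Primary Efficacy Outcome Statistical Evaluation, gives the decision: "non-inferiority will be established, according to the pre-specified overall study success criteria, if this proportion is not less than 70" per cent.

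Four other provisions bear on the rule:

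- On analysis sets, the plan says "Non-inferiority will be established if both the ITT and PP analyses agree" (under Populations Examined).
- On imputation, it says "Missing data for the ITT population will be handled through Last Observation Carried Forward (LOCF"), in the section on missing values.
- On the two success rates, it says "A comparison of proportions test will be performed to evaluate if the two success proportions (GVL vs. EVRL) are equivalent to support the conclusion" drawn from the main analysis, at p<0.05 (under Comparison of Proportions).
- On mean change in VAS, it adds a two-sample t-test "to evaluate for equivalency to support the support the conclusion of the proportion of successes evaluation", also at p<0.05 (under Change Scores).

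The sample size of 43 is copied from the intended enrolment of the EVRL study (Rationale for Sample Size). No error level or power is attached to it. Indication for Use says the results are meant to support a 510(k) submission.

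**The concern.** A non-inferiority conclusion means the data exclude a true deficit as large as the margin, at a small stated risk of error. That requires a confidence limit or a test. Here the cut on the estimate is the margin itself, so sampling error in the GVL rate is ignored. Sampling error in the EVRL rate is ignored too, because its observed 75% is entered as a constant. The null hypothesis is written down but never tested.

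This is the primary success rule, and its output is the claim intended for the regulator. A pass would be reported as established non-inferiority even where the data are compatible with a much larger loss than the plan calls acceptable.

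**Working it through.** **Inputs.** From the plan: N = 43 (Sample Size); EVRL success rate 75%, margin 5 points and limit 70% (Justification for Study Success Criteria); rule of observed proportion at least 70% (Proportion of Successes). Assumed: the EVRL denominator, which the plan does not give.

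**1. The plan's own limit.** 75% - 5 points = 70%, as stated. 0.70 × 43 = 30.1, and 30/43 = 69.8% fails, so 31/43 = 72.1% is the smallest pass.

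**2. Pass rate of the rule.** With all 43 endpoints observed, P(X ≥ 31) for X ~ Binomial(43, p):

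| True GVL rate | Relation to a true EVRL rate of 75% | Pass rate |
|---|---|---|
| 60% | 15 points worse | 7.0% |
| 65% | 10 points worse | 20.9% |
| 70% | on the margin | 45.6% |
| 75% | equal | 73.7% |

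**3. Missing endpoints.** Suppose m endpoints are missing and LOCF carries baseline forward, so each counts as a non-success. The denominator stays 43 and the pass rate is P(X ≥ 31) for X ~ Binomial(43 - m, p):

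| m | p = 0.70 | p = 0.75 |
|---|---|---|
| 1 | 36.3% | 64.9% |
| 2 | 27.5% | 54.8% |
| 3 | 19.6% | 44.0% |

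If PP drops those same subjects, its bar falls to 30/42, 29/41 or 28/40. ITT is then the binding set and the joint pass rates are those shown.

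**4. ITT and PP with complete data.** If all 43 endpoints are observed, PP drops 1 to 5 subjects at random, and the same 70% cut applies to both sets (the likeliest reading), the joint pass rate at a true 70% is 42.3% to 45.6%.

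**5. What a test would require.** Even with 70% taken as a fixed limit, at p = 0.70 P(X ≥ 37) = 0.0125 and P(X ≥ 36) = 0.0311. The exact cut is therefore 37/43 at one-sided 0.025 and 36/43 at one-sided 0.05.

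**6. What a minimum pass shows.** The exact (Clopper-Pearson) 95% interval for 31/43 is 56.3% to 84.7%. Against assumed EVRL counts, with Newcombe limits for the difference and an uncorrected chi-square (also an assumption, since the plan names no statistic):

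| Assumed EVRL | Difference (points) | 95% lower limit (points) | 90% lower limit (points) | Chi-square p |
|---|---|---|---|---|
| 32/43 | -2.3 | -20.5 | -17.7 | 0.81 |
| 33/44 | -2.9 | -21.0 | -18.2 | 0.76 |
| 30/40 | -2.9 | -21.2 | -18.4 | 0.76 |
| 45/60 | -2.9 | -20.3 | -17.6 | 0.74 |

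The 95% lower limit is about four times the margin, while the difference test is comfortably non-significant.

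**7. What an interval rule would require.** For all four assumed EVRL counts, the smallest GVL count with a lower limit above -5 points is 38/43 (two-sided 95%) or 37/43 (two-sided 90%). Given those counts, power is P(X ≥ 38) = 2.6% or P(X ≥ 37) = 6.1% at a true 75%, and 35.9% or 52.9% at a true 85%. With a smaller assumed EVRL set of 15/20 the counts rise to 39/43 and 38/43.

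**8. Size needed for a formal claim.** For 80% power at a true 75% against a fixed 70%, one-sided 0.025: n = [(1.960 × √(0.70 × 0.30) + 0.842 × √(0.75 × 0.25)) / 0.05]², about 638. For two groups both at 75%: n = (1.960 + 0.842)² × 2 × 0.75 × 0.25 / 0.05², about 1,178 per group.

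**The case against.** The best defence is that the rule is pre-specified, transparent and reasoned: a stated reference rate, a stated margin, and the strategy the plan says supported clearance K191257. That explains the choice, but precedent sets no error level.

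It can also be said that any point-estimate cut placed at the margin passes roughly half the time there, so 45.6% is generic. That is true, and the rule does reject clearly worse devices: it passes only 7.0% of the time at a true 60%. But 20.9% at 65% is still high for a device at twice the permitted deficit.

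The supportive comparison might be read as an equivalence test using the 5-point margin, since the plan says it evaluates equivalence and names no statistic. This reading is possible, so the chi-square p-values above are illustrative. Under either reading the test only supports the conclusion and does not gate success. If it is an ordinary difference test, a non-significant result does not show equivalence.

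The ITT/PP requirement and LOCF do make the rule somewhat stricter. ITT and PP are nearly the same subjects under the same cut, and LOCF still leaves about 20% at the margin with three endpoints missing while also lowering the chance that an equal device passes. Few endpoints should be missing, because the assessment comes within 3 minutes of the single session.

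**Conclusion.** The concern holds. The primary rule does not test the stated null, and nothing else in the plan limits the risk of a false non-inferiority claim to a small stated level. The 45.6% rests on 43 observed endpoints and a true EVRL rate of 75%. The 31/43 cut and the exact interval need no assumption about EVRL. The two-sample figures depend on assumed EVRL counts, but the conclusion is the same in every scenario tried. This must be corrected before the result is described as non-inferiority.

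**What to change.** 1. **Restate the rule.** Keep N = 43 and the 70% cut, but call it a descriptive performance target (at least 31 of 43). State its pass rates with all endpoints observed: 46% at a true 70%, 21% at 65%, 74% at 75%. Remove the claims of established non-inferiority and equivalence consistently from Expected Results, Study Design, Overall Study Success Criteria (including the 70% to 80% range), Justification for Study Success Criteria, Proportion of Successes, Comparison of Proportions and Change Scores.
2. **Report intervals.** Give the exact 95% interval for the GVL rate and an interval for GVL minus EVRL. The statistician already receives both data sets as Groups A and B, so the difference can be computed as A minus B and its direction assigned at unblinding.
3. **Reserve the claim.** Allow a non-inferiority statement only if the lower limit of the difference is above -5 points in both ITT and PP, at a confidence level and sidedness fixed in advance (the plan's p<0.05 gives no sidedness). Tie the hypotheses and the ITT/PP sentence to this rule only, or delete them. Confirm that the EVRL data allow both sets to be formed. Say that the interval covers sampling error only, since the comparison is open-label, non-randomised and historical.

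The cost is coordinated wording edits and two interval calculations, with no new subjects. The price is a more modest claim in the 510(k) submission: the rule in item 3 is rarely attainable at this size, so the restated target in item 1 is the practical route.
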